**Table 6 List of Excluded Medications**

Treatment	Washout period
Topical medication (including corticosteroid, retinoids or vitamin A or D analog preparations, tacrolimus, calcineurin inhibitor, topical H1 and H2 antihistamines, tar preparations, keratolytics, topical antimicrobials, other medicated topical agents) or herbal preparation	2 weeks
Methotrexate, cyclosporin, acitretin, alitretinoin, Fumaric acid esters, and corticosteroids or any other immunosuppressant or immunomodulating drugs	4 weeks
Anti-tumor necrosis factor/interleukin (IL-12/IL-23) and IL-17 or any other mAbs	3 months or 5 half -lives
Cyclophosphamide	6 months
Phototherapy or PUVA	4 weeks
Antibiotics and antivirals	Topical: 2 weeks Systemic: 4 weeks
Other investigational drugs	30 days or 5 half-lives (whichever is longer)
Live attenuated vaccines	3 months

Abbreviations: mAbs = monoclonal antibodies; PUVA = psoralen and ultraviolet A.

## **Appendix 6            Contraceptive Guidance and Collection of Pregnancy Information**

### **Definitions:**

#### ***Woman of childbearing potential (WOCBP)***

A woman is considered fertile following menarche and until becoming postmenopausal unless permanently sterile (see below).

If fertility is unclear (eg, amenorrhea in adolescents or athletes) and a menstrual cycle cannot be confirmed before first dose of study intervention, additional evaluation should be considered.

#### ***Women in the following categories are not considered WOCBP***

1. Premenarchal
2. Premenopausal female with 1 of the following:
  - Documented hysterectomy.
  - Documented bilateral salpingectomy.
  - Documented bilateral oophorectomy.

For individuals with permanent infertility due to an alternate medical cause other than the above, (eg, mullerian agenesis, androgen insensitivity), Investigator discretion should be applied to determining study entry.

Note: Documentation can come from the study center personnel's: review of the subject's medical records, medical examination, or medical history interview.

3. Postmenopausal female:
  - A postmenopausal state is defined as no menses for 12 months without an alternative medical cause. A high follicle stimulating hormone (FSH) level in the postmenopausal range may be used to confirm a postmenopausal state in women not using hormonal contraception or hormonal replacement therapy (HRT). However, in the absence of 12 months of amenorrhea, a single FSH measurement is insufficient.
  - Females on HRT and whose menopausal status is in doubt will be required to use 1 of the non-estrogen hormonal highly effective contraception methods if they wish to continue their HRT during the study. Otherwise, they must discontinue HRT to allow confirmation of postmenopausal status before study enrollment.

## Contraception Guidance

### *Male subjects*

- Male subjects with female partners of childbearing potential are eligible to participate if they agree to ONE of the following (during the protocol-defined time frame in Section 5.1):
  - Are abstinent from penile-vaginal intercourse as their usual and preferred lifestyle (abstinent on a long-term and persistent basis) and agree to remain abstinent.
  - Agree to use a male condom plus partner use of a contraceptive method with a failure rate of <1% per year when having penile-vaginal intercourse with a WOCBP who is not currently pregnant.
- In addition, male subjects must refrain from donating sperm for the duration of the study and for 220 days (which includes the duration of relevant exposure plus the duration of sperm cycle) after the last dose of study treatment.
- Male subjects with a pregnant or breastfeeding partner must agree to remain abstinent from penile-vaginal intercourse or use a male condom during each episode of penile penetration for the duration of the study and for 220 days (which includes the duration of relevant exposure plus the duration of sperm cycle) after the last dose of study treatment.

### *Female subjects*

Female subjects of childbearing potential are eligible to participate if they agree to use highly effective methods of contraception consistently and correctly as described in the table below.

## Highly Effective Contraceptive Methods

Highly Effective Contraceptive Methods That Are User Dependent a  Failure rate of <1% per year when used consistently and correctly.

Combined (estrogen and progestogen containing) hormonal contraception associated with inhibition of ovulation
 
 
• Oral.
 
• Intravaginal.
 
• Transdermal.
 

Progestogen only hormonal contraception associated with inhibition of ovulation
 
 
• Oral.
 
• Injectable.
 

Highly Effective Methods That Are User Independent a

Implantable progestogen only hormonal contraception associated with inhibition of ovulation
 
 
• Intrauterine device (IUD).
 
• Intrauterine hormone-releasing system (IUS).
 
 
Bilateral tubal occlusion.

Vasectomized Partner  A vasectomized partner is a highly effective birth control method provided that the partner is the sole male sexual partner of the WOCBP and the absence of sperm has been confirmed. If not, an additional highly effective method of contraception should be used.

Sexual Abstinence  Sexual abstinence is considered a highly effective method only if defined as refraining from heterosexual intercourse during the entire period of risk associated with the study treatment. The reliability of sexual abstinence needs to be evaluated in relation to the duration of the study and the preferred and usual lifestyle of the subject.

NOTES:  a Typical use failure rates may differ from those when used consistently and correctly. Use should be consistent with local regulations regarding the use of contraceptive methods for subjects participating in clinical studies.

### Pregnancy Testing:

- Women of childbearing potential should only be included after a confirmed menstrual period and a negative highly sensitive serum pregnancy test at Screening and urine pregnancy test on Day 1 (prior to study treatment administration).
- Women of childbearing potential should refrain from donating oocytes for assisted reproduction during this period.
- Additional pregnancy testing should be performed as mentioned in the Schedule of Activities (see Section 1.3).
- Pregnancy testing will be performed whenever a menstrual cycle is missed or when pregnancy is otherwise suspected. Positive urine pregnancy test result should be confirmed with serum test.

## Collection of Pregnancy Information

### *Male subjects with partners who become pregnant*

- The Investigator will attempt to collect pregnancy information on any male subject's female partner who becomes pregnant while the male subject is in this study. This applies only to male subjects who receive study treatment.
- After obtaining the necessary signed informed consent from the pregnant female partner directly, the Investigator will record pregnancy information on the appropriate pregnancy form and submit it to the Sponsor within 24 hours of learning of the partner's pregnancy. The female partner will also be followed to determine the outcome of the pregnancy. Information on the status of the mother and child will be forwarded to the Sponsor. Generally, the follow-up will be no longer than 6 to 8 weeks following the estimated delivery date. Any termination of the pregnancy will be reported regardless of fetal status (presence or absence of anomalies) or indication for the procedure.

### *Female subjects who become pregnant*

- The Investigator will collect pregnancy information on any female subject who becomes pregnant while participating in this study. Information will be recorded on the appropriate form and submitted to the Sponsor within 24 hours of learning of a subject's pregnancy.
- The subject will be followed to determine the outcome of the pregnancy. The Investigator will collect follow-up information on the subject and the neonate and the information will be forwarded to the Sponsor. Generally, follow-up will not be required for longer than 6 to 8 weeks after the delivery date. Any termination of pregnancy will be reported, regardless of fetal status (presence or absence of anomalies) or indication for the procedure.
- While pregnancy itself is not considered to be an AE or SAE, any pregnancy complication or elective termination of a pregnancy will be reported as an AE or SAE. A spontaneous abortion is always considered to be an SAE and will be reported as such.
- Any post-study pregnancy related SAE considered reasonably related to the study treatment by the Investigator will be reported to the Sponsor as described in Section 8.3.5. While the Investigator is not obligated to actively seek this information in former subjects, he or she may learn of an SAE through spontaneous reporting.
- Any female subject who becomes pregnant while participating in the study will be withdrawn from the study.

## **Appendix 7            Genetics**

### **Use/Analysis of DNA/mRNA**

- Genetic variation may impact a subject's response to study treatment, susceptibility to, and severity and progression of disease. Variable response to study treatment may be due to genetic determinants that impact drug absorption, distribution, metabolism, and excretion; mechanism of action of the drug; disease etiology; and/or molecular subtype of the disease being treated. Therefore, where local regulations and IRB/IEC allow, a blood sample will be collected for DNA analysis from consenting subjects.
- DNA/mRNA samples will be used to study disease pathogenesis and to determine potential genetic biomarkers of response to treatment. Genetic research may consist of the analysis of 1 or more candidate genes or the analysis of genetic markers throughout the genome or analysis of the entire genome.
- DNA samples will be analyzed for genetic analysis.
- The samples may be analyzed as part of a multi-study assessment of genetic factors involved in the response to study treatment or study treatments of this class to understand study disease or related conditions.
- Samples will be sent to the designated laboratory where they will be stored according to ICH GCP and GLP requirements with adequate measures to protect confidentiality. Genetic analysis using DNA/mRNA samples may be performed by additional third party (eg, a university Investigator) designated by the Sponsor. The results of genetic analyses may be reported in the CSR or in a separate study summary.
- The samples may be retained while research on study treatment or study treatments of this class or indication continues as described in the ICF.

## Appendix 8 Clinical Global Impression

Category	Change in modified JDA severity index total score for GPP	and/or	Category description
Very much improved	Reduction by 3 or >points	or	Clear or almost clear of signs of GPP
Much improved	Reduction by 1 or 2 points	or	At least one of the following: 
 
• Area of erythema with pustules (%) reduced by <math>\leq 30\%</math>
 
or
 
• Clinically meaningful improvement in at least 2 other components of the modified JDA severity index for GPP (area of erythema, area of edema, fever, WBC, CRP, Alb)
 

Minimally improved	0 points (no change)	and	At least one of the following: 
 
• Area of erythema with pustules (%) reduced by <math>\leq 20\%</math>
 
or
 
• Clinically meaningful improvement in at least 1 other components of the modified JDA severity index for GPP (area of erythema, area of edema, fever, white blood cell [WBC], C-reactive protein [CRP], Alb)
 

No change	0 points (no change)	and	Not meeting the other criteria of “minimally improved”
Worsened	$\geq + 1$ point	-	Not applicable

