## 4.0 STUDY DESIGN

### 4.1 Overall Design

This is an open-label, single arm, multiple dose study to assess the clinical efficacy, as well as the safety, tolerability, and PK of multiple doses of ANB019 in subjects with GPP.

The screening period will be up to 42 days (6 weeks) prior to administration of study drug on Day 1. Written informed consent will be obtained from each subject prior to initiating any study related procedures. All screening procedures will be conducted in accordance with the Schedule of Activities (see Section 1.3).

On Day 1, subjects who meet the entry criteria will receive a 750 mg IV dose of ANB019 in an open-label manner followed by 3 doses of 100 mg SC administered on Days 29, 57, and 85. Subjects will leave the study center after completion of the 5 hours postdose assessments following IV administration and the 3 hours postdose assessments after the first and second SC injections and with the Investigator's approval. Subjects with any ongoing AEs or SAEs at the time of scheduled discharge from the study center should remain at the study center until the Investigator has determined that these events have resolved or are deemed as not clinically significant.

After completing Day 1 assessments, the subjects will return to the study center for follow-up visits on Days 3, 8, weekly from Day 8 to Day 29, and every other week up to Day 85, and monthly for 12 weeks to monitor changes in disease activity, safety, and tolerability. In addition, subjects will be contacted via phone by study staff to assess for safety (eg, AEs and changes in concomitant medications) on Days 36, 50, 64, and 78.

Subjects who are nonresponders will be early terminated 4 weeks after the 750 mg IV dose administration. A nonresponder is defined as:

- “No change” on CGI: 0 points change in JDA total score and not meeting “other criteria” for minimally improved.
- “Worsened” based on CGI:  $\geq 1$ -point increase in JDA total score.

Disease activity (response to study treatment) will be evaluated using the CGI scale according to the modified JDA severity index, change in total BSA as measured by modified JDA index affected by GPP, systemic manifestations and laboratory findings as per modified JDA severity index, GPPPGA scale, and PASI score (if PP is present). In addition, change in serum cytokines (including but not limited to IL-8) will be recorded. Quality of life (QoL) will be assessed using the DLQI.

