5. STUDY DESIGN

5.1. GENERAL DESCRIPTION

This is an open-label, single arm, multiple dose study to assess the clinical efficacy, as well as the safety, tolerability, and PK of multiple doses of ANB019 in subjects with GPP.

The screening period will be up to 42 days (6 weeks) prior to administration of study drug on Day 1. Written informed consent will be obtained from each subject prior to initiating any study related procedures. All screening procedures will be conducted in accordance with the Schedule of Activities (see Section 1.3 in the protocol). On Day 1, subjects who meet the entry criteria will receive a 750 mg IV dose of ANB019 in an open-label manner, followed by 3 doses of 100 mg SC administered on Days 29, 57, and 85.

Subjects will leave the study center after completion of the 5 hours postdose assessments following IV administration and the 3 hours postdose assessments after the first and second SC injections and with the investigator's approval. Subjects with any ongoing AEs or SAEs at the time of scheduled discharge from the study center should remain at the study center until the Investigator has determined that these events have resolved or are deemed as not clinically significant.

After completing Day 1 assessments, the subjects will return to the study center for follow-up visits on Days 3, 8, weekly from Day 8 to Day 29, every other week up to Day 85, then monthly for 12 weeks to monitor changes in disease activity, safety, and tolerability. In addition, subjects will be contacted via phone by study staff to assess for safety (e.g., AEs and changes in concomitant medications) on Days 36, 50, 64, and 78.

Subjects who are non-responders at Week 4 will be early terminated 4 weeks after the 750 mg IV dose administration. A non-responder is defined as a subject who experiences:

- "No change" on Clinical Global Impression (CGI): 0 points change in JDA total score and not meeting "other criteria" for minimally improved.
- "Worsened" based on CGI: ≥1-point increase in JDA total score.

[figure not shown]
Disease activity (response to study treatment) will be evaluated using the CGI scale according to the mJDA severity index, change in total area of erythema with pustules, erythema, and edema as measured by modified JDA index, systemic manifestations and laboratory findings as per modified JDA severity index, GPPPGA scale, and PASI score (if PP is present). Quality of life (QoL) will be assessed using the DLQI.

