17. EFFICACY OUTCOMES

17.1. PRIMARY EFFICACY

17.1.1. RESPONSE BASED ON CLINICAL GLOBAL IMPRESSION SCALE

The primary efficacy endpoint is the proportion of subjects achieving clinical response at Weeks 4 and 16. The clinical response is defined as a composite score which considers both the CGI and reduction in the mJDA score (compared to Baseline) at that visit, and is classified as "Very much improved", "Much improved", or "Minimally improved" on the 5-point CGI scale (see **Table C. Clinical Global** Impression).

Page 10 of 43

Table C. Clinical Global Impression

Change in mJDA Severity Index Total score	and/ or	CGI Category description	CGI scale and Responder status
Reduction by 3 or >3 points	or	Clear or almost clear of signs of GPP	Very much improved
			Responder
Reduction by 1 or 2 points	or	At least one of the following: Area of erythema with pustules (%) reduced by ≤30%, or Clinically meaningful improvement in at least two other components of the mJDA severity index for GPP (area of erythema, area of edema, fever, white blood cells (WBC), C-reactive protein (CRP) and serum albumin (Alb)).	Much improved Responder
0 points (no change)	and	At least one of the following: Area of erythema with pustules (%) reduced by ≤20%, or Clinically meaningful improvement in at least one other component of the mJDA severity index for GPP (area of erythema, area of edema, fever, WBC, CRP, Alb)	Minimally improved Responder
0 points (no change)	and	Not meeting the CGI criteria of "minimally improved"	No change Non- responder
Increased $\geq + 1$ point		Not applicable	Worsened Non- responder

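### The CGI table lets a subject whose mJDA total rises by 1 point or more also meet 'Much improved', and states no precedence, so primary responder status is not uniquely defined

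*Protocol*

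**What the plan says.** The primary efficacy endpoint is the proportion of subjects in one of the three improved CGI categories at Week 4 and at Week 16 (Protocol 3.0 and 9.4.4.1; SAP 3.1.1). The categories are set out in Protocol Appendix 8 and repeated in SAP Table C (SAP 17.1.1). Each row pairs a change in the modified JDA (mJDA) total with a description:

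- *Very much improved*: a fall of 3 points or more, **or** "Clear or almost clear of signs of GPP".
- *Much improved*: "Reduction by 1 or 2 points", **or** at least one of two descriptions. One begins "Area of erythema with pustules (%) reduced by" and sets a limit of ≤30%. The other is "Clinically meaningful improvement in at least 2 other components of the modified JDA severity index for GPP" (SAP: "Clinically meaningful improvement in at least two other components of the mJDA severity index for GPP").
- *Minimally improved* and *No change*: a change of 0 points, **and** a description that is met or not met.
- *Worsened*: a rise of 1 point or more; the description column is marked not applicable.

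SAP 5.1 repeats the last row in its non-responder definition: "based on CGI: ≥1-point increase in JDA total score". Protocol 4.1 has the same definition and attaches a consequence: "Subjects who are nonresponders will be early terminated 4 weeks after the 750 mg IV dose administration". SAP 17.1.2 adds that a Week 4 non-responder keeps that status at Week 16.

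**The concern.** The *or* branches of the two top rows put no limit on the direction of the total, while *Worsened* depends on the total alone. The rows are therefore not mutually exclusive. The overlap also crosses the line that matters, because one row is a responder row and the other a non-responder row. The documents give no order of evaluation and no best-row or worst-row rule.

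Where both rows are met, the choice falls to the rater or the programmer, in an open-label single-arm study. At Week 4 the same choice decides whether the subject meets the non-responder definition that leads to early termination and fixes Week 16 status. SAP 17.1.4 plans no sensitivity analysis of the primary variable, so no planned summary would show how much depends on the choice.

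**Working it through.** **Inputs.** Seven mJDA items: pustular erythema, total erythema and edema scored 0–3; fever, WBC, CRP and albumin scored 0–2 (Protocol Appendix 9; SAP Table D). Entry total >6 on one route (Protocol 5.1). About 10 subjects (Protocol 9.2; SAP 5.2).

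**Check of the scale.** Maximum total = 3 × 3 + 4 × 2 = 17, which agrees with the top of the severe band.

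**Can both rows be met?** Scores are in the order pustules, erythema, edema, fever, WBC, CRP, albumin.

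1. *Component route.* Baseline 2,2,1,1,1,0,0 = 7. Visit 2,2,1,0,0,1,2 = 8. Change = 8 − 7 = +1, so *Worsened*. Fever and WBC each fall by one score point, so two other components improve and *Much improved* is also met, if those falls are judged clinically meaningful. The documents do not define that term.
2. *Pustule-area route.* Baseline 2,2,1,0,1,1,0 = 7. Visit 2,2,1,0,1,2,0 = 8. Change = +1, so *Worsened*. Let pustular area go from 45% to 35%: 10 percentage points, or 10/45 = 22% relative, with the item score still 2. Taken as written (a reduction of ≤30%), this meets *Much improved* and needs no judgement of clinical meaning.
3. *Very much improved.* With baseline total 7 or more and all three skin scores 0, a rise needs a total of at least 8. The four systemic items reach at most 4 × 2 = 8, so all four must be at maximum. The overlap is possible but narrow. It is wider if almost clear allows low skin scores, or if a subject enters with a low total on the GPPPGA route.

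**How many score profiles overlap?** There are 4³ × 3⁴ = 5,184 profiles. I paired every eligible baseline with every follow-up profile and took a lower item score as a stand-in for clinically meaningful improvement (an assumption).

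| Baseline restriction | Pairs with total up ≥1 | Of these, ≥2 other items lower |
|---|---|---|
| Total >6 | 6,929,358 | 3,312,557 (48%) |
| Total >6, pustule score ≥2, erythema score ≥1 | 2,341,255 | 822,650 (35.1%) |
| Second row, each item moving ≤1 point | 293,091 | 58,620 (20.0%) |

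For total >6, 678 of the 6,929,358 rising pairs (0.01%) have all skin scores 0, and 95,034 (1.4%) have all skin scores ≤1. These are unweighted counts of possible profiles, not probabilities. In the 20.0% set at least two items fall by one point each, so at least three must rise for the total to go up: five or more of the seven items move, in opposite directions.

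**Effect on the endpoint.** SAP 17.1.3 divides by all enrolled subjects. One reclassified subject moves the rate by 1/10 = 10 percentage points, for example from 7/10 = 70% to 6/10 = 60%. If the subject is called *Worsened* at Week 4, SAP 17.1.2 makes the subject a non-responder at Week 16 as well. If called *Much improved*, the subject continues and can be a responder at Week 16.

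**The case against.** The strongest reply is that the plan already answers the question. Protocol 4.1 and SAP 5.1 call a rise of 1 point or more non-response without exception. The not-applicable entry in the *Worsened* row can be read as switching the descriptions off once the total rises. SAP 17.1.1 also describes response as a composite that considers the reduction in mJDA as well as the CGI. This shows a likely intent, and the fix below follows it. It does not remove the conflict. Those sections restate the *Worsened* row and do not say that it overrides a *Much improved* row that is also met. SAP 17.1.2 falls back on the CGI alone when the baseline mJDA total is missing, which implies a CGI rating separate from the total.

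A second reply is that by-subject listings and plots of CGI category and mJDA change would expose a favourable category beside a risen total. They would help an alert reader, but they do not say which classification counts.

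A reader might also infer more than the documents support:

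- *That the overlap is common.* The 35.1% and 20.0% figures depend on the baseline restriction and weight all transitions equally. Protocol 2.1 and 2.2 describe skin and systemic signs occurring together, which argues against frequent opposing movements.
- *That Very much improved is equally exposed.* It is reached only in rare profiles, and rarer still if signs of GPP include fever and laboratory findings.
- *That a subject would be recorded in two categories.* Protocol 8.1.1 has the change categorised on one scale, so presumably one category is entered per visit. The defect is that the criteria do not determine which.

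**Conclusion.** The point holds for *Much improved* and, in rare profiles, for *Very much improved*. The rules in both documents can assign opposite primary-endpoint status to the same data, and no text resolves this. The size is 10 percentage points per affected subject at Week 4, and possibly the same at Week 16, assuming 10 subjects in the denominator. The number of affected subjects may be zero; the documents do not allow an estimate. The component-route example assumes that a one-point fall in an item score is judged clinically meaningful. The pustule-area example assumes the ≤30% limit is read as written.

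The study is exploratory and tests no hypothesis, so no error rate is at issue. A descriptive responder count must still be determined by the data, and here it is not. The conflict should be resolved before database lock.

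**What to change.** Before database lock:

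1. Make the rows of SAP Table C and Protocol Appendix 8 mutually exclusive for the endpoint analysis by a stated precedence consistent with the non-responder definition in Protocol 4.1 and SAP 5.1: a rise of 1 point or more in the mJDA total is not counted as response in the primary analysis.
2. Derive the category by program, in that order, from the recorded mJDA values and the CGI rating. SAP 17.2.1.1 says the eCRF captures the scores and actual values of all seven items.
3. List every subject who meets both a responder row and the *Worsened* row, and show the response rate under the alternative classification.

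The sponsor must reconcile the Week 4 early-termination text with the table. This review does not propose which clinical rule should apply there.

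The cost is one condition in the derivation, one listing, and a response rate that may be less favourable.
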